A Randomized Controlled Trial Comparing Retropubic KIM sling to TVT Exact Midurethral Sling

NCT number: NCT04985799

Document Date: April 15, 2021

A Randomized Controlled Trial Comparing Retropubic KIM sling to TVT Exact Midurethral Sling

BACKGROUND / RATIONALE

Midurethral slings (MUS) are recognized as a minimally invasive treatment of stress urinary incontinence (SUI). The retropubic route of MUS placement has a cure rate of 89.1%¹ with long term subjective cure rates ranging from 51-88%.² The Neomedic Knotless Incontinence Mesh (KIM) sling is a tension-free macroporous monofilament polypropylene knotless mesh designed to be resistant to elongation and deformation over time.³ The KIM sling also offers a reusable trocar, which results in less waste and cost- savings. KIM sling trocars are available for the retropubic route or trans-obturator (TOT) route.

While studies have been performed comparing the TOT approach of the KIM sling to other slings, no studies have been performed to date with the retropubic (RP) approach. The RP and TOT approaches to MUS have been shown to be equivalent in the treatment of SUI.⁴ Since the same mesh material of the KIM sling is used for both the TOT and RP approach, we can conclude that the RP route would show similar treatment success rates.

A type 1 macroporous (> 75um) polypropylene mesh is the most appropriate material for vaginal implantation.⁵ Currently in our practice we use the Gynecare TVT Exact sling, which meets these requirements. However, Chapple et al suggest that the design and weave of synthetic mesh material can also have a significant effect on efficacy and safety;⁵ therefore, the novel design of the KIM may be beneficial to reduce complications. If we can show there is similar efficacy with the RP approach of the KIM sling to the TVT Exact, there will be benefit of reduced costs and the potential for less complications. With this study, our aim is to show non-inferiority of the KIM sling to the Gynecare TVT Exact.

Given that the midurethral sling has been proven to be effective at treating stress urinary incontinence, and that lightweight, large pore mesh has less adverse effects, we propose a randomized trial to show noninferiority of the Neomedic KIM sling compared to the well-studied Gynecare TVT Exact sling. The study population will be patients that have clinically demonstrated SUI and have already chosen to pursue midurethral sling surgery for treatment. Validated questionnaires will be used to evaluate the subjective response to treatment, as a subjective outcome most closely relates to patient experience and satisfaction.

STUDY AIMS

Primary aim: Our primary aim is to assess to the non-inferiority of the retropubic Neomedic KIM sling compared to the Gynecare TVT Exact sling at 6 weeks.

We hypothesize that the KIM sling will be non-inferior to the TVT exact sling at 6 weeks postoperatively.

Secondary aims:

- To assess the non-inferiority in effectiveness of the retropubic Neomedic KIM sling compared to Gynecare TVT Exact at 1 year post-operatively.
- To assess safety of the Neomedic KIM sling compared to the Gynecare TVT Exact sling with regards to mesh exposure and reoperation for urinary retention or mesh complications at 1 year postoperatively.

STUDY DESIGN & METHODS

This is a randomized controlled, double-blinded, non-inferiority trial comparing effectiveness and safety of the Neomedic KIM midurethral sling to Gynecare TVT exact midurethral sling

Study Population

Inclusion criteria:

- Women ≥21 years based on medical chart review
- Diagnosis of SUI or mixed urinary incontinence based on medical chart review
- Objective evidence of SUI as indicated by positive cough stress test or urodynamic stress incontinence during urodynamic testing within the last year prior to enrollment. Medical chart will be reviewed.
- Planning surgery for SUI with/without POP surgery

Exclusion criteria:

- Current Pregnancy, desire for future childbearing, or ≤12 months postpartum at the time of enrollment
- Prior history of surgery for SUI based on medical chart review
- Bladder capacity <200mL on Urodynamic testing or PVR >150mL on Urodynamic testing or bladder scan.
- Non-ambulatory
- Current genitourinary fistula or urethral diverticulum based on pre-operative exam in the medical chart.

Outcome measures

*Primary outcome:*_SUI treatment success at 6 weeks post-operatively. Treatment success will be based on a composite outcome of:

- Response of "No" on UDI-6 (subscale of PFDI-20), question #3 OR if answered "yes", must indicate "no bother"
- No re-treatment with a pessary, other incontinence device or repeat surgery (urethral bulking, Burch urethropexy, sling, or other procedure)

Secondary outcomes:

- 1. SUI treatment success at 1 year
 - a. Uses same composite outcome criteria as primary outcome
- 2. Complication rates at 1 year
 - a. Urinary retention
 - b. Mesh exposure- determined by physical exam at 1 year
 - c. Reoperation for urinary retention or mesh complications thru 1 year

Baseline characteristics will be used to define the study population. Variables to be collected:

- Age- number
- Race- Caucasian/ Black/ American Indian or Alaskan Native/ Asian/ Pacific Islander/ Other
- Ethnicity- Hispanic/ non-Hispanic
- BMI- number
- POP-Q points- number

- Smoking status- non-smoker/ current/ former
- Past medical history
 - Diabetes- yes/no
 - Charlson comorbidity index- number
- Past surgical history
 - Prior hysterectomy- yes/no
 - Prior prolapse surgery- yes/no
 - Prior surgery for SUI- yes/no
 - Prior bladder tack surgery- yes/no

Data of concurrent surgical treatment at the time of intervention, which will be used to define the study population:

- Hysterectomy
- Anterior repair
- Posterior repair
- Apical suspension
 - Uterosacral ligament suspension
 - Sacrospinous ligament fixation
 - Sacrocolpopexy

Study Intervention

The KIM sling is a tension-free Knotless Incontinence Mesh (KIM) sling. Any patient with female stress urinary incontinence can be a candidate for this sling. The KIM system provides support under the urethra to decrease stress urinary incontinence in patients, similar to other slings. As opposed to other slings on the market, KIM-specific benefits include being knotless which could decrease the friction between the permanent product and patient tissue which could decrease the risk of erosion or bacteria. The sling is placed via a short, outpatient procedure where a small vaginal incision is made with two exit points through the skin. Patients can be discharged on the same day of surgery. Of note, the KIM sling also allows for a reusable trocar system.⁸

Study participants will be randomized to receive the Gynecare TVT Exact sling or the Neomedic KIM sling in the operating room by a trained Urogynecologist.

Participating surgeons will undergo training on how to place KIM sling. This includes but is not limited to teaching or device representatives in the operating room for intraoperative questions. These surgeons already have experience in placing Gynecare TVT Exact slings, as this is the current standard of care. The KIM sling has subtle differences in placement which will be addressed at the training. All surgeons in the study will undergo one training together prior to the start of the study and will have individual help from device representatives.

Randomization, Concealment, and Blinding

The randomization schema will be created using Stata, and this schema will be uploaded into the REDCap database, where randomization will be performed and maintained. This technique will be used to prevent selection bias by concealing the allocations from those assigning participants until the moment of assignment. Randomization will occur in the operating room prior to performing the procedure. Assignment codes will remain within REDCap with access to the randomization for the research investigators. The randomization codes will not be broken unless knowing the sling type affects

the patient's health or if there is a complication postoperatively that requires knowing the type of sling placed.

Masking (Blinding)

This study will be double blinded. While the providers in the operating room placing the sling will not be able to be blinded, the subjects and data collectors will be blinded to the treatment assignment.

Study Procedures and Schedule

Procedures	Screening	Baseline	Intervention	6 weeks visit	6 month visit	1 year visit
Eligibility Assessment	Х					
Informed Consent		Х				
Medical History		Х				
Study Intervention			Х			
PFDI-20		Х		Х	Х	Х
PGI-I				Х	Х	Х
Symptom Questionnaire				Х	Х	Х
Physical Exam				Х		Х

Screening (within 6 months prior to enrollment)

Pre-screening will be performed through a provider visit, obtaining history, physical exam and urodynamics study if needed, where the patient will be evaluated for if they are eligible for a sling. If the patient is deemed eligible, they will verbally be consented to be screened for and contacted regarding the research study. The research coordinator will screen for eligibility and will contact the patient to further discuss the study. This screening will take place within 6 months prior to enrollment.

Enrollment / Baseline (Day 0)

- Informed consent
- PDFI-20
- Obtain baseline characteristics (medical history)

Visit 1 (Surgical intervention- within 6 months of enrollment)

• Intervention- randomized to treatment

Visit 2 (6 ± 2 weeks from intervention)

- PFDI-20
- PGI-I
- Symptom questionnaire
- Physical exam
- Adverse event / SAE assessment

Visit 3- phone (6 ± 2 months)

- PFDI-20
- PGI-I
- Symptom questionnaire

• Adverse event / SAE assessment

Final Visit (1 year ± 2 months)

- PFDI-20
- PGI-I
- Symptom questionnaire
- Physical exam
- Adverse event / SAE assessment

Statistical Analysis Plan

Strategies that Apply to all the Specific Aims

- To help ensure replicability of the research, the analysis plans will be reviewed and finalized prior to collection of data (a priori). For each specific aim, the analysis plans specify detailed steps for obtaining estimates of population parameters (e.g., treatment effects) and for making inferences.
- Descriptive graphical and tabular methods will be used to characterize the participants, visualize the data and examine relationships among variables.
- For each specific aim, the analyses will focus on the magnitude and direction of point- and interval-estimates of the population parameters of interest. To indicate precision, all statistical estimates of population parameters will be tabulated along with corresponding confidence intervals (CI) or standard errors (SE). The CI will be interpreted as the set of potential values of the population parameter that are most compatible with the observed data.
- All hypothesis tests yielding p-values that are deemed to be not statistically significant will be reported as being inconclusive. The proposed statistical analysis strategy acknowledges that no p-value can reveal the plausibility, presence, truth, or importance of an association or effect.

Plans for Aim 1:

To assess the non-inferiority in the effectiveness of the retropubic Neomedic KIM sling compared to Gynecare TVT Exact sling at 6 weeks, we will present the 2-by-2 contingency tables on SUI treatment success counts. Then, we will perform the one-sided hypothesis test of H_0 : (PTVT – PKIM) > Δ vs H_a : (PTVT – PKIM) $\leq \Delta$, where PTVT is the proportion of success counts in the TVT sling group, PKIM is the proportion of success counts in the Neomedic KIM sling group, and Δ is the conjectured inferiority margin. We will use the chi-squared test to test the above hypothesis. In addition, we will provide the 95% confidence interval of PTVT – PKIM.

Plans for Aims 2:

We will perform a similar analysis for Aim 1 to compare effectiveness at 1 year.

To evaluate the complication rates of the retropubic KIM sling compared to the TVT Exact at 6 weeks and 1 year post-operatively, we will also present 2-by-2 contingency tables on complication counts (for urinary retention, mesh exposure and reoperation for mesh complications and urinary retention). We will perform a two-sided test on comparing the proportions of complications between KIM sling and TVT Exact sling groups. Again, such a test will be performed by using the chisquared test. In addition, we will provide the 95% confidence interval of the differences of the proportions between these two groups.

Sample Size Rationale

Our statistical power calculation was based on prior studies showing retropubic sling success rate being 89-95%¹⁻⁵ and using 12-15% non-inferiority margin⁶⁻⁹. We based our sample size estimate on the following: 90% sling success with a 14% non-inferiority margin and 80% power, assuming a 20% dropout rate. If there is truly no difference between the standard and experimental treatment (90% in both groups), then 114 patients are required to be 80% sure that the upper limit of a one-sided 95% confidence interval (or equivalently a 90% two-sided confidence interval) will exclude a difference in favor of the standard group of more than 14%. To assume a 20% dropout rate, we needed to enroll 144 participants for our primary outcome of treatment success at 6 weeks postoperatively. Sample size calculator used was https://www.sealedenvelope.com/power/binary-noninferior/.

Recruitment Strategy

Once a patient has been seen by a Urogynecology physician and plans to have sling surgery for SUI, the physician will notify the study team to screen for eligibility. After the study team determines eligibility, the patient will then be approached by the study team for recruitment.

Retention Strategy

The 6 week, 6 month and 1 year visits will be incentivized monetarily in order to enhance retention. Subjects will receive \$25 with completion of the 6 week visit and \$75 with completion of the 1 year visit. The 6 month visit will be performed over the phone and/or with REDCap surveys in order to reduce the burden on the participant.

Screen Failures

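### Outcome 2b counts mesh exposure only as found at the 1-year exam, so the 1-year rate omits exposures that resolved or were treated earlier, and no count of women exposed by 1 year is planned

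*Combined protocol and SAP*

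**What the plan says.** Outcome measures, Secondary outcomes, item 2 lists three complication rates at 1 year. Item 2b is "Mesh exposure- determined by physical exam at 1 year". Item 2c is "Reoperation for urinary retention or mesh complications thru 1 year". The second secondary aim compares the safety of the two slings "with regards to mesh exposure and reoperation for urinary retention or mesh complications at 1 year postoperatively".

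The analysis is in Plans for Aims 2, which sets out "To evaluate the complication rates of the retropubic KIM sling compared to the TVT Exact at 6 weeks and 1 year post-operatively". It provides 2-by-2 tables for retention, mesh exposure and reoperation, a two-sided chi-squared test, and a 95% confidence interval for the difference. It does not say whether the 1-year exposure count is prevalent or cumulative, or what happens at 1 year to an exposure found earlier.

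In Study Procedures and Schedule, physical exams fall at 6 weeks and 1 year only, and the 6-month contact is by phone. "Adverse event / SAE assessment" is listed at all three follow-up contacts, but no text links those reports to 2b.

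**The concern.** Two adjacent safety outcomes use different time frames. Reoperation accumulates to 1 year, while exposure is read off one exam. A mesh exposure can be treated or can resolve, so prevalence at the final exam can be lower than the proportion of women who had an exposure during the year.

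Mesh exposure is named in the secondary safety aim. The Background gives the potential for fewer complications as part of the case for KIM, and Study Intervention links the knotless design to a possibly lower erosion risk. A reader will take a 1-year exposure rate to mean how many women had an exposure by 1 year, and the plan does not produce that number. Adding the 6-week and 1-year tables does not recover it: a persistent exposure would count twice, and one that came and went between exams would not count at all.

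**Working it through.** **Step 1. Where each course of exposure is counted, as the plan is worded.**

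| Course of the exposure | 6-week table | 2b at 1 year | 2c |
|---|---|---|---|
| Seen at 6 weeks, still present at 1 year | yes | yes | no |
| Seen at 6 weeks, resolved without reoperation before 1 year | yes | no | no |
| Seen at 6 weeks, reoperated and resolved before 1 year | yes | no | yes, pooled |
| Arises after 6 weeks, present at 1 year | no | yes | no |
| Arises after 6 weeks, reoperated and resolved before 1 year | no | no | yes, pooled |
| Arises after 6 weeks, resolves without reoperation before 1 year | no | no | no |

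Pooled means counted together with reoperation for retention. Four of the six courses are missing from 2b, but only the last is missing from every named outcome. Those cases may still be recorded at an adverse event assessment, or in the symptom questionnaire, whose content is not given.

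**Step 2. Time between exams.** Nominal: 52.2 − 6 = about 46 weeks. With the visit windows, the shortest gap is 10 months − 8 weeks = about 35 weeks and the longest is 14 months − 4 weeks = about 57 weeks. The one scheduled contact in between is by phone.

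**Step 3. The plan's own figure.** The documents state no number for mesh exposure. The primary sample size does reproduce. With 90% success in both arms, a 14-point margin, one-sided 5% and 80% power:

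n per arm = 2 × 0.90 × 0.10 × (1.645 + 0.842)² / 0.14² = 56.8, so 57, or 114 in total.

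Dividing by 0.80 for dropout gives 142.5, so 143, or 144 with equal arms. None of this depends on 2b.

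**Step 4. Illustration of the 1-year table read alone.** Every rate here is an assumption. Take cumulative exposure of 6% and 2% (a 4-point difference), and let r be the share of exposures no longer present at the 1-year exam. Take 57 evaluable women per arm, which assumes equal allocation and that the 20% dropout planned for 6 weeks also holds at 1 year.

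- Reported difference = 6 × (1 − r) − 2 × (1 − r)
- Expected exposures, both arms = 57 × (0.06 + 0.02) × (1 − r)

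| r in both arms | Reported rates | Difference | Expected exposures |
|---|---|---|---|
| 0 | 6% vs 2% | 4 points | 4.6 |
| 25% | 4.5% vs 1.5% | 3 points | 3.4 |
| 50% | 3% vs 1% | 2 points | 2.3 |
| 75% | 1.5% vs 0.5% | 1 point | 1.1 |

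With unequal r: 6 × 0.50 − 2 × 0.75 = 1.5 points, and 6 × 0.75 − 2 × 0.50 = 3.5 points.

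**Step 5. Precision.** Newcombe 95% intervals: 3/57 vs 1/57 is 3.5 points (−4.8 to 12.7); 2/57 vs 1/57 is 1.8 points (−6.2 to 10.3). The two intervals overlap almost entirely.

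In Step 4, r includes exposures already counted in the 6-week table or in 2c. The shrinkage therefore describes the 1-year table taken by itself. It does not measure the last row of Step 1, which cannot be quantified from the documents.

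**The case against.** The strongest reply has three parts.

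First, the wording of 2b may name the method of ascertainment rather than the time frame, and its parent heading speaks of complication rates at 1 year, so a cumulative count may be intended. This is possible. But the line names a single exam, the next line marks its cumulative scope explicitly, and no rule carries earlier findings forward. Followed as written, 2b is a prevalence.

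Second, prevalence at a scheduled exam given to both arms is a legitimate safety measure, more uniform than a count that draws on a phone contact. This stands, and it is why the exam results should be kept. It does not supply the missing count.

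Third, most of the information is recorded elsewhere and events will be few. This also stands, and it limits the point to what the reported rate means.

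A reader might infer that the trial fails to capture early exposures at all. The 6-week table, 2c and the adverse event assessments show otherwise. A reader might also infer that a true difference of 4 points would shrink to 1 point and be lost to the trial. The documents give neither exposure rates nor resolved shares, and that shrinkage includes cases already counted in other tables.

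**Conclusion.** As worded, the 1-year exposure rate omits women whose exposure resolved or was treated before the final exam, and no single count of women exposed by 1 year is planned for an outcome named in the safety aim. This rests on the text alone.

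The size of the undercount is unknown. Under the assumed rates, 1.1 to 4.6 exposures would be expected across both arms, and the comparison is imprecise whichever definition is used. The consequence is for the reported rates and their meaning, not for power, the sample size or the primary outcome.

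Nothing in the documents suggests that exposures resolve at different rates in the two arms, so a bias favouring either sling should not be inferred. Nor does the point extend to urinary retention (2a): the documents do not define retention, so its time frame is a separate question.

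**What to change.** In Outcome measures and in Plans for Aims 2, define 2b as at least one mesh exposure from surgery through 1 year, found at the 6-week exam, the 1-year exam, an adverse event assessment, or a reoperation for mesh exposure. Report the proportion per arm and the 95% confidence interval of the difference.

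State the denominator: all randomized women who received a sling, with women who had a 1-year exam as a sensitivity analysis. The first counts women with no 1-year exam and no recorded exposure as unexposed, so it leans low. The second drops exposures recorded in women who missed that exam. For example, take 72 women in an arm, 57 examined at 1 year with 3 exposures among them, and 1 exposure among the other 15. The main result is 4/72 = 5.6% and the sensitivity result is 3/57 = 5.3%.

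Keep the 6-week and 1-year exam prevalences as separate results.

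The cost is outcome wording and a denominator rule. No visits or participants are added, because the exams and adverse event assessments are already scheduled. The Statistical Analysis Plan section has the analysis plans finalized before data collection, so this can be settled then.

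There are two downsides. Reported rates may be higher. Exposures found between exams are ascertained less uniformly and may be classified unblinded, because the 6-month contact is by phone and the code may be broken "if there is a complication postoperatively that requires knowing the type of sling placed". The exam-only results alongside address this.

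### Planned concurrent prolapse surgery could be used to balance and weight the sling comparison, but the plan uses concurrent surgery only to describe the population (a low-priority improvement, not an error)

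*Combined protocol and SAP*

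**What the plan says.** - **Eligibility.** The inclusion criteria admit women "Planning surgery for SUI with/without POP surgery", with no limit on the type or number of added procedures.
- **Recording.** Under Outcome measures, after the baseline variables, the protocol lists hysterectomy, anterior repair, posterior repair and three apical procedures. It introduces them as "Data of concurrent surgical treatment at the time of intervention, which will be used to define the study population". No other use is given.
- **Randomisation.** The section on randomization, concealment and blinding says: "The randomization schema will be created using Stata, and this schema will be uploaded into the REDCap database". It names no stratification factor, block size, minimisation or allocation ratio. On timing: "Randomization will occur in the operating room prior to performing the procedure". The masking paragraph adds that the operating team cannot be blinded.
- **Analysis.** For Aim 1, "we will present the 2-by-2 contingency tables on SUI treatment success counts" and "We will use the chi-squared test to test the above hypothesis". The plans for Aim 2 repeat this approach for success at 1 year and for complications. The only general provision for covariates is descriptive: "Descriptive graphical and tabular methods will be used to characterize the participants, visualize the data and examine relationships among variables". No stratified, adjusted or subgroup analysis by concurrent surgery appears.
- **Sample size.** The rationale rests on "90% sling success with a 14% non-inferiority margin and 80% power, assuming a 20% dropout rate".

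**The concern.** The primary outcome combines a woman's own report of stress leakage with absence of re-treatment. It is reasonable to suppose, though the documents do not say so, that a second pelvic operation in the same session is related to that report. If so, concurrent surgery is a prognostic factor that can be known before allocation and will be collected in some form, yet plays no part in the design or the comparison.

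Two things are then at stake. Some precision is lost, because variation that the factor explains stays in the error term. And in the one trial that is run, the arms may differ by chance in their share of concurrent surgery, which moves the estimated sling difference. The SAP intends its analyses to be fixed before data collection, so an adjustment added after such an imbalance is seen would not have the standing of a pre-specified one.

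**Working it through.** **Inputs from the Sample Size Rationale:** 90% success in both arms, 14-point margin, one-sided 5% level, 80% power, 20% dropout, 114 evaluable, 144 enrolled.

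**Assumptions (not in the documents):** 1:1 allocation; simple randomisation; share of women with concurrent surgery *q* = 30–70%; difference in success between women with and without it *e* = 0–15 points.

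**Step 1. The plan's own figures.** Per arm, n = (1.645 + 0.842)² × 2 × 0.9 × 0.1 / 0.14² = 6.185 × 0.18 / 0.0196 = 56.8, so 57, or 114 in total. For dropout, 57 / 0.8 = 71.25, so 72 per arm, or 144. Both figures reproduce.

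**Step 2. Chance imbalance.** The SD of the between-arm difference in share is √(2q(1−q)/n). Probabilities come from 400,000 simulated binomial draws per row.

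| n per arm | q | SD (points) | 1.96 SD | P(≥10 points) | P(≥20 points) |
|---|---|---|---|---|---|
| 57 (evaluable) | 0.3 or 0.7 | 8.6 | 16.8 | 26% | 2% |
| 57 (evaluable) | 0.5 | 9.4 | 18.4 | 30% | 3% |
| 72 (randomised) | 0.3 or 0.7 | 7.6 | 15.0 | 17% | 1% |
| 72 (randomised) | 0.5 | 8.3 | 16.3 | 21% | 1.5% |

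**Step 3. Effect on the estimate.** Shift in PTVT − PKIM = imbalance × *e*. For a 1.96-SD imbalance at 57 per arm and q = 0.5:
- e = 0: no shift
- e = 5 points: 18.4 × 0.05 = 0.9 points
- e = 10 points: 18.4 × 0.10 = 1.8 points
- e = 15 points: 18.36 × 0.15 = 2.8 points

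At q = 0.3 or 0.7 the last three are 0.8, 1.7 and 2.5 points.

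For scale, the standard error of the difference is √(2 × 0.9 × 0.1 / 57) = 5.6 points. The SD of the shift is 9.37 × *e*, or 0.47, 0.94 and 1.40 points. As a share of the sampling variance, (0.47/5.62)², (0.94/5.62)² and (1.40/5.62)² give about 0.7%, 2.8% and 6.2%.

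**Step 4. Operating characteristics.** There were 200,000 simulated trials per scenario, with 57 per arm, q = 0.3, 0.5 and 0.7, and e = 0, 5, 10 and 15 points. Non-inferiority was declared when the one-sided 95% Wald upper limit was below 14 points, the criterion in the sample size text.

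| Design and analysis | Type I error | Power |
|---|---|---|
| Simple randomisation, crude difference | 5.4–5.6% | 79.9–80.5% |
| Stratified randomisation, Mantel-Haenszel difference | 5.6–5.9% | 80.4–82.8% |
| Simple randomisation, Mantel-Haenszel difference | 5.7–6.0% | 80.4–82.7% |

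The mean error of the crude estimate was under 0.05 points in every scenario. Its type I error was the same at e = 0 as at e = 15, so the small excess over 5% belongs to the Wald interval and not to concurrent surgery. The largest gain in power from stratified design plus analysis was 82.8 − 80.3 = 2.5 points, and the smallest was essentially zero. Part of that gain reflects the slightly higher type I error of the stratified Wald interval.

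**The case against.** The case for leaving the plan alone is strong. An unadjusted comparison in a randomised trial is valid, and its confidence interval already carries the uncertainty from chance imbalance. Nothing in the documents says that prolapse surgery affects stress leakage, and without that premise it is one baseline variable among many. All of this stands. It limits the point to a modest gain in precision but does not remove it, because the change is almost free.

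Several stronger readings are tempting and are not supported:

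- *The comparison is biased or invalid.* The simulation shows otherwise.
- *The schema is unstratified.* The text is silent on this. It is fair to say only that no balancing is described.
- *An imbalance could not be separated from the sling effect.* The procedures are recorded, so an imbalance would be visible and could be adjusted for. What is missing is the pre-specification.
- *Retention is more exposed than success.* The documents give no retention rate, so this cannot be sized.
- *The trial should show non-inferiority for the sling alone.* That is not an aim. At an assumed 50% share, about 28 women per arm would have a sling alone. The standard error is then √(0.18/28) = 8.0 points, the 95% half-width is 15.7 points, and power against 14 points is Φ(14/8.02 − 1.645) = Φ(0.10), about 54%.

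In the other direction, a reader might say that setting the shift against the 14-point margin understates it. The upper limit clears the margin only if the observed difference is below about 14 − 1.645 × 5.62 = 4.8 points, and 1.8–2.8 points is roughly 40–60% of that room. This is correct for a trial that draws such an imbalance. It takes a 1-in-20 draw together with an assumed 10–15 point effect, and averaged over randomisations the crude analysis keeps its 80% power.

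**Conclusion.** The point holds as a low-priority improvement, not an error. The plan permits and records concurrent prolapse surgery, describes no balancing on it, and compares the arms without it. If the factor is not prognostic, nothing is lost. If it changes success by 5–15 points in 30–70% of women, the plan forgoes between nothing and about 3 points of power. It also accepts about a 1-in-20 chance that the estimate moves by roughly 1 to 3 points or more through imbalance in this factor. The share, the effect, the 1:1 ratio and simple randomisation are all assumptions. The facts about what the plan does and does not describe are not.

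**What to change.** **If randomisation has not started:**
- Add a baseline field for planned concurrent prolapse surgery (yes/no), completed before randomisation. The inclusion item is met either way, so it does not supply this field.
- Generate the Stata schema in permuted blocks stratified by that field, and say so in the randomisation section.
- In the plans for Aims 1 and 2, pre-specify a Mantel-Haenszel stratum-weighted risk difference with its confidence interval for success at 6 weeks and 1 year.

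**If randomisation has started:** make only the analysis change, before outcomes are seen by arm. Classify women by the surgery planned before allocation, taken from the chart, and not by the surgery performed. The recorded list refers to procedures at the time of intervention. Allocation comes before the procedure and the operators know it, so surgery performed could be influenced by the assignment.

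Separate estimates for sling-alone and sling-plus-prolapse women are optional and should be labelled descriptive.

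**Cost:** one allocation stratum, one baseline field and a sentence or two in the SAP, with the sample size unchanged at 114 evaluable and 144 enrolled. The statistical price is a stratified Wald interval whose one-sided error runs a little further above nominal: about 5.6–5.9% with stratified randomisation (5.7–6.0% for the analysis-only change), against 5.4–5.6% for the crude interval.
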